### **5.2.2 Worsening of pre-existing conditions**

Expected fluctuations or expected deterioration of the underlying disease will not be recorded as an AE. If progressive disease occurs and is associated with symptoms or meets one of the seriousness criteria (see section 8.4.1), the signs and symptoms of progressive disease will be reported as an adverse event or a serious AE (if applicable).

A pre-existing condition present at baseline, which remains unchanged during the trial, does not need to be recorded as adverse event. However, any worsening of any pre-existing baseline condition should be reported as an adverse event. Example of worsening of a preexisting condition that should be recorded as an AE are given below;

- Worsening of condition meets the criteria for an SAE
- Action is taken with the investigational drug (i.e. dose is reduced or treatment is discontinued or increased)
- Treatment is required (concomitant medication is added or changed)
- The investigator believes a patient has shown a clear deterioration from baseline symptoms

### 5.2.3 Dose-limiting Toxicity (DLT)

A dose-limiting toxicity (DLT) is defined as an adverse event or laboratory abnormality that is: a) considered to be related to BIBW 2992 as used in regimen U or M and b) meets any of the following criteria:

#### a) Hematologic adverse reaction:

- 1) CTCAEv3 Grade 4 neutropenia (ANC, including bands,  $<500/\text{mm}^3$ ) for more than 7 days; or
- 2) CTCAEv3 Grade 3 or 4 neutropenia of any duration associated with fever  $>38.3^\circ\text{C}$ .
- 3) CTCAEv3 Grade 3 thrombocytopenia (platelet count  $< 50,000 - 25,000/\text{mm}^3$ ); or
- 4) All other hematological toxicities of CTCAE Grade  $\geq 3$  leading to an interruption of treatment with both study drugs for more than 14 days until recovery to baseline or Grade 1, whichever is higher.

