### 1.2.2 Temozolomide

Temozolomide (TMZ) is an orally administered, second generation imidazotetrazine prodrug with essentially 100% oral bioavailability. TMZ spontaneously converts to the active alkylating agent 5-(3-methyltriazene-1-yl) imidazole-4-carboximide (MTIC) with extensive tissue distribution, including penetration of the blood-brain barrier and the cerebrospinal fluid. TMZ has notable antitumour activity against recurrent GBM (R08-1057), recurrent anaplastic astrocytoma, and advanced malignant melanoma, and other refractory cancers. TMZ has shown activity when added to radiotherapy for treatment of newly diagnosed GBM (R08-1056).

TMZ is rapidly absorbed and spontaneously converts to the active metabolite MTIC. Maximum plasma concentrations are observed 30 to 90 minutes after oral intake, and the plasma half-life is approximately 2 hours, with some delayed absorption when taken with food. Pharmacokinetics in the CSF compared with plasma showed an AUC of approximately 20% of the AUC. Patients usually tolerate TMZ well; mild to moderate adverse effects are nausea and vomiting that are usually easily controlled with standard antiemetic drugs, constipation, and some fatigue. The most serious and dose-limiting toxicity, observed in less than 10% of patients, is noncumulative myelosuppression, particularly thrombocytopenia occurring 3 to 4 weeks after treatment start,

TMZ is indicated for the treatment of patients with newly diagnosed glioblastoma multiforme concomitantly with radiotherapy and subsequently as monotherapy treatment. TMZ is also

indicated for treatment of malignant glioma, showing recurrence or progression after standard therapy. In the concomitant phase TMZ is administered orally at a dose of 75 mg/m^2 daily for 42 days concomitant with focal radiotherapy (60 Gy administered in 30 fractions) without dose reductions, but delay or discontinuation of TMZ can be considered weekly according to haematological and non-haematological side effect criteria. The TMZ is usually continued throughout the 42 day concomitant period (up to 49 days) in absence of adverse reaction.

Four weeks after completing the TMZ + Radiotherapy phase, TMZ is administered for up to 6 cycles of monotherapy treatment. The dose in cycle 1 (monotherapy) is 150 mg/m^2 once daily for 5 days followed by 23 days without treatment. At the start of Cycle 2, the dose is escalated to 200 mg/m^2 in absence of side effects.

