##### Substance (INN): Temozolomide (TMZ) – Regimen M only

Pharmaceutical form:	Hard gelatine capsules
Source:	Provided by sponsor
Unit strength:	5, 20, 100 and 140 mg

Dose:	RT concomitant phase: 75 mg/m  daily Maintenance phase (4 weeks after end of RT): - cycle 1: 150 mg/m  , - from cycle 2 up to cycle 6: 200 mg/m  (if tolerated)
Duration of use:	RT concomitant phase: Continuous daily dosing for 42 days Maintenance phase: Four weeks after completing radiotherapy, once daily for 5 days followed by 23 days without treatment.
Route of administration:	Oral (swallowed)
Posology:	Once daily

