### 4.1.4.1.2 Dose reduction scheme for BIBW: Regimen U and M

If a patient develops side effect that meets criteria for DLT (for definition refer to Section 5.2.3) regardless of treatment cycle, treatment with BIBW 2992 must be paused. If all drug-related adverse events recover to CTCAE Grade 1 or baseline (whichever is higher) within 14 days of stopping treatment with BIBW 2992, treatment may be resumed with dose reductions according to Table 4.1.4.1.2: 1. Otherwise, the patient will be taken off study. Exceptions to this are patients who derive obvious clinical benefit according to the investigator's judgment. These patients could be considered in agreement with BI's Trial Clinical Monitor (TCM) for further treatment.

If a patient need to dose reduced BIBW 2992 during RT, the dose of BIBW 2992 during the maintenance period will need to be discussed and decided on a case to case base between BI Trial Clinical Monitor and the investigator at site (keep BIBW2992 reduced daily dose or change as planned for 40mg BIBW2992 daily)

Table 4.1.4.1.2: 1 Dose reduction scheme for Regimen M and U

Treatment prior to treatment pause and dose reduction BIBW (mg)	Dose reduction		
	1 st DLT BIBW (mg)	2 nd DLT BIBW (mg)	3 rd DLT
20	Off-study		
30	20	Off-study	
40	30	20	Off-study

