### 5.2.4 Maximum Tolerated Dose (MTD)

7. The MTD is defined as:
8. The dose of BIBW 2992 when given concomitantly with TMZ and RT (Regimen M) or BIBW 2992 when given concomitantly with radiotherapy (Regimen U) which is one dose tier below that dose at which two or more out of six patients experienced drug-related DLTs during the 6 weeks (42-day) RT treatment period. DLT experienced after the start of the maintenance treatment period will be examined separately. At the MTD, no more than one patient out of six patients may experience DLT, i.e., MTD is defined as the

highest dose studied for which the incidence of DLT is no more than 17% (i.e. 1/6 patients).

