### 5.2.6 Safety laboratory investigations

Blood samples for safety analysis will be collected at the time points specified in the Flow Chart and analyzed in the investigator's local laboratories. Safety laboratory examinations will include hematology, biochemistry, urine examination and a pregnancy test. In case of neutropenia, blood will be examined as clinically indicated at the discretion of the investigator until recovery.

The following parameters will be determined

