## **Delays in Radiotherapy**

Delays should be avoided if at all possible. There is a potential risk of bleeding in patients with low platelets, and if a platelet count  $< 25 \times 10^9/l$  is recorded, radiotherapy should be delayed until the platelets have recovered to  $> 50 \times 10^9/l$ .

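### The haematologic DLT list omits Grade 4 thrombocytopenia, and its catch-all item requires stopping two study drugs, which one-drug Regimen U cannot satisfy

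*Protocol*

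**What the plan says.** Section 5.2.3 gives one DLT list for both regimens; an event must also be judged related to BIBW 2992. The haematologic part has four items. Items 1 and 2 cover prolonged Grade 4 neutropenia and Grade 3 or 4 neutropenia with fever. Item 3 is "CTCAEv3 Grade 3 thrombocytopenia", with the platelet range printed as below 50,000 down to 25,000/mm³ and no duration condition. Item 4 takes every other haematologic toxicity of Grade 3 or higher, but only when it is "leading to an interruption of treatment with both study drugs for more than 14 days".

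Section 4.1.1 lists "Temozolomide (TMZ) – Regimen M only", and Section 4.2 places radiotherapy under concomitant therapy. Regimen U therefore has one study drug.

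Three other parts of the plan depend on the list:

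- **MTD (Section 5.2.4):** "At the MTD, no more than one patient out of six patients may experience DLT".
- **Dose pause (Section 4.1.4.1.2):** when a DLT occurs, "regardless of treatment cycle, treatment with BIBW 2992 must be paused".
- **Analysis (SAP Section 5.1):** the primary endpoint is investigator-determined DLT under Section 5.2.3, with no change to the definition.

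**The concern.** A DLT list should not rank a worse grade of the same toxicity as less limiting. Read literally, a platelet count of 40,000/mm³ is an immediate DLT, while a count of 15,000/mm³ alone is not. Yet Section 10.6 treats a count below 25 × 10⁹/l as the level at which "radiotherapy should be delayed until the platelets have recovered".

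The toxicity matters most in Regimen M. Section 1.2.2 describes TMZ's most serious, dose-limiting toxicity as myelosuppression, "particularly thrombocytopenia occurring 3 to 4 weeks after treatment start".

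Three decisions are at stake: the DLT count that sets the MTD, the immediate BIBW 2992 pause, and reporting as a significant adverse event (Section 5.2.5). Item 4 also cannot act as an early trigger. It is met only after more than 14 days off both drugs, whereas Section 4.1.4.1.2 takes a patient off study, absent an agreed exception, if recovery has not occurred within 14 days.

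**Working it through.** **1. Apply items 3 and 4 literally to a BIBW 2992-related platelet count.**

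| Regimen | Platelet grade | Study drug(s) stopped 0 days | 10 days | 15 days |
|---|---|---|---|---|
| U (one drug) | 3 | DLT | DLT | DLT |
| U (one drug) | 4 | not DLT | not DLT | not DLT |
| M (both drugs stopped) | 3 | DLT | DLT | DLT |
| M (both drugs stopped) | 4 | not DLT | not DLT | DLT |

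If only TMZ is stopped in Regimen M, as Section 4.1.4.2 allows for TMZ side effects, item 4 is not met either. In Regimen U the same wording excludes every other Grade 3 or higher cytopenia outside items 1 and 2, such as anaemia.

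**2. Look for a repair elsewhere.**

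- The catch-all in Section 5.2.3(b) item 6 is limited to non-haematologic events.
- The protocol's first DLT table (Section 7.3.1) drops the relatedness condition but still selects events by the Section 5.2.3 criteria.
- The SAP refers back to Section 5.2.3.

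None of these brings Grade 4 platelets in.

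**3. Ask whether a patient can be missed.** A patient with a related count also recorded between 25,000 and 50,000 is already a DLT under item 3. The loss is confined to Grade 4 events with no such count.

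- Section 6.2.2.1 schedules safety laboratory tests on days 1, 8, 15, 29 and 42, so days 16 to 28 (13 days) have none.
- Three to four weeks after a day 1 start is days 22 to 29, so day 29 is the only scheduled count in that window. A first abnormal recorded count can therefore already be Grade 4.
- The next scheduled count is day 42.
- Section 5.2.6 provides for extra counts ("blood will be examined as clinically indicated at the discretion of the investigator until recovery") only in neutropenia.

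**4. Reproduce the MTD threshold.** 1/6 = 16.7%, which matches the 17% in Section 5.2.4. Two of six is 33%, so one uncounted patient can move a dose from failing to passing.

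**5. Illustrate the effect (all rates assumed).** For a counted DLT rate p,

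P(at most 1 of 6) = (1 − p)⁶ + 6p(1 − p)⁵.

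Take a true rate of 30% at 40 mg, given that the 40 mg cohort is opened and evaluated.

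| Points uncounted | Counted p | P(at most 1 of 6) |
|---|---|---|
| 0 | 0.30 | 0.118 + 0.303 = 0.420 |
| 1 | 0.29 | 0.442 |
| 2 | 0.28 | 0.464 |
| 5 | 0.25 | 0.534 |

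Each uncounted point adds about 2 points. With all DLTs counted, true rates of 25% and 20% give 0.534 and 0.655.

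The escalation step in Table 4.1.4.1.1: 1 behaves in the same way. P(escalate) = P(0 of 3) + P(1 of 3) × P(0 of 3). At 30% this is 0.343 + 0.441 × 0.343 = 0.494; with 5 points uncounted it is 0.600.

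**The case against.** The strongest reply is that this is a drafting slip with little practical reach.

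- **Recovery counts.** Section 10.6 holds radiotherapy below 25 × 10⁹/l until platelets exceed 50 × 10⁹/l. Showing recovery needs repeat counts, and a rising count passes through the Grade 3 band. This narrows the gap considerably. It does not close it: no repeat count is scheduled, a count can go from below 25 to above 50 between samples, and a Grade 4 count after the last fraction has no radiotherapy left to hold.
- **The laboratory gap hides both grades.** True, and the rewording recovers no unseen count. But the gap is what allows a first recorded count to be Grade 4 with no earlier Grade 3 count.
- **Weekly TMZ review.** Section 1.2.2 mentions weekly decisions on haematological criteria, and Section 4.1.4.2 defers to the TMZ product information. Counts in Regimen M may therefore be more frequent than the visit schedule shows. This stands as a limit.
- **Both can be read as all assigned drugs.** That is the workable reading, but it is not the text, and about five sites would each have to adopt it.
- **Size.** Section 1.2.2 puts TMZ's dose-limiting myelosuppression below 10% of patients. The lost events are a subset: Grade 4, related to BIBW 2992, with no Grade 3 count. The 5-point row is illustration only. Section 1.2.1 lists no cytopenia among the most frequent BIBW 2992-related events in Phase I monotherapy, so little is expected in Regimen U.
- **Safeguards.** DLT is investigator-determined, escalation needs the sponsor monitor's agreement, and the 40 mg cap lies below the 50 mg monotherapy MTD. These make a wrong decision less likely. They work by overriding the definition, not by correcting it.

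**Conclusion.** The point holds, and the definition should be fixed. As written, Grade 4 thrombocytopenia is a DLT in Regimen M only after more than 14 days off both drugs, and in Regimen U item 4 can never apply. Confidence in the reading of the text is high. The effect on the MTD cannot be sized from the documents: they give no Grade 4 platelet rate and no frequency for Grade 4 events without a Grade 3 count. The direction is known: DLTs can only be under-counted, so the MTD can only be biased upwards. The gain of about 2 points per uncounted point rests on an assumed true DLT rate near 30%, six evaluated patients, and the 40 mg cohort being reached.

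**What to change.** Amend Section 5.2.3(a) in two places:

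- **Item 3:** Grade 3 or higher thrombocytopenia (platelets below 50,000/mm³).
- **Item 4:** interruption of the study drug or drugs for more than 14 days, meaning BIBW 2992 in Regimen U, and BIBW 2992 and TMZ in Regimen M.

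The pause rule in Section 4.1.4.1.2 and the primary endpoint in SAP Section 5.1 already point to Section 5.2.3, so both inherit the change without separate wording. SAP Section 7.8.1 cites Section 5.2.2 for the DLT definition and should be corrected to 5.2.3 at the same time.

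The cost is a short protocol amendment. No visits, samples or data fields are added, and the DLT count can only stay the same or rise.

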#### b) Non-hematologic adverse reaction:

1. CTCAEv3 Grade  $\geq 3$  nausea or vomiting is occurring despite appropriate use of standard anti-emetics for at least three days.
2. CTCAEv3 Grade  $\geq 3$  diarrhoea despite appropriate use of standard anti-diarrheal therapy for at least three days.
3. CTCAEv3 Grade  $\geq 3$  rash despite standard medical management as outlined in Section 4.2.3 and lasting  $>7$  days.
4. CTCAEv3 Grade  $\geq 2$  cardiac left ventricular function.
5. CTCAEv3 Grade  $\geq 2$  worsening of renal function as measured by serum creatinine, newly developed proteinuria, or newly developed decrease in glomerular filtration rate.
6. All other non-hematological toxicities of CTCAEv3 Grade  $\geq 3$

### 5.2.4 Maximum Tolerated Dose (MTD)

7. The MTD is defined as:
8. The dose of BIBW 2992 when given concomitantly with TMZ and RT (Regimen M) or BIBW 2992 when given concomitantly with radiotherapy (Regimen U) which is one dose tier below that dose at which two or more out of six patients experienced drug-related DLTs during the 6 weeks (42-day) RT treatment period. DLT experienced after the start of the maintenance treatment period will be examined separately. At the MTD, no more than one patient out of six patients may experience DLT, i.e., MTD is defined as the

highest dose studied for which the incidence of DLT is no more than 17% (i.e. 1/6 patients).

### 5.2.5 Significant Adverse Events

DLTs are termed significant Adverse Events.

Although rare, drug-induced liver injury is under constant surveillance by sponsors and regulators and is considered a protocol-specified significant adverse event. Timely detection, evaluation, and follow-up of laboratory alterations of selected liver laboratory parameters to distinguish an effect of the underlying malignancy on liver function from other causes are important for patient safety. The following are considered as Protocol-specified significant events:

Hepatic injury defined by the following alterations of liver parameters:

- For patients with normal liver function (ALT, AST and bilirubin within normal limits) at baseline an elevation of AST and/or ALT  $\geq 3$  fold ULN combined with an elevation of bilirubin  $\geq 2$  fold ULN measured in the same blood draw sample. Patients showing these lab abnormalities need to be followed up according to APPENDIX 10.8 of this clinical trial protocol and the "DILI checklist" provided in the ISF
- For patients with abnormal liver function at baseline an elevation of AST and/or ALT  $\geq 5$  fold ULN combined with an elevation of bilirubin  $\geq 2$  fold ULN measured in the same blood draw sample. Patients showing these lab abnormalities need to be followed up according to APPENDIX 10.8 of this clinical trial protocol and the "DILI checklist" provided in the ISF.

Protocol-specified significant events are to be reported in an expedited manner similar to Serious Adverse Events, even if they do not meet any of the seriousness criteria - for details please see chapter 8.4.1.

If the investigator determines any protocol-specific significant event is related to study drug, the administration of the study drug must be managed according to section 4.1.4.1.2 of the protocol.

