##### **4.1.4.1.1 Dose escalation scheme for BIBW**

Initially, 3 evaluable patients will be treated per dose level. As soon as one patient experiences a DLT (see section 5.2.3), 3 new patients will be treated at that dose level, to treat a minimum of 6 evaluable patients. If no other patients experience DLT the dose will be escalated to the next level and 3 further patients treated. If two or more of six patients

experience DLT, three additional patients will be treated at one dose tier below unless six have already been treated at that dose tier.

The MTD (see section 5.2.4) is the highest dose at which no more than one of 6 patients experiences DLT. Once the MTD is determined, patient enrolment at higher dose tiers will be suspended.

The MTD cohort in each Regimen may be expanded to include up to 12 patients.

Intra-patient dose escalation will not be permitted.

The first three patients at each dose level will be treated and observed for at least 6 weeks (42 days) during RT before the next cohort of new patients are treated at the next higher dose level (Table 4.1.4.1.1: 2 and 4.1.4.1.1: 3).

Table 4.1.4.1.1: 1 Rules for dose escalation for regimen M and U

Number of Patients with DLT at a Given Dose Level	Escalation Decision Rule
0 out of 3	Enter 3 patients at the next dose level.
1 out of 3	Enter at least 3 more patients at this dose level. - If 0 of these 3 patients experience DLT, proceed to the next dose level. - If 1 or more of this group suffer DLT, then dose escalation is stopped. Three (3) additional patients will be entered at the next lower dose level if only 3 patients were treated previously at that dose.
$\geq 2$ out of 3	Dose escalation will be stopped. Three (3) additional patients will be entered at the next lower dose level if only 3 patients were treated previously at that dose.

The decision regarding dose escalation steps will only be made after agreement with the sponsor's Trial Clinical Monitor (TCM).

Dose escalation and entry of patients into the next dose cohort will begin only after accrual of the required minimum number of patients has been achieved and all patients in the cohort are considered following completion of 6 weeks BIBW2992 treatment ((42 days ) during RT). Patients who are not treated until the end of these 6 weeks for any reasons other than DLT will be replaced (section 6.3.1).

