### **6.3.1 Replacement of patients**

Patients who do not receive study treatment during the chemoradiation phase for more than 5 consecutive days or more than 8 non-consecutive days for any reasons other than DLT will be replaced.

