7.4 PRIMARY ENDPOINTS

DLT during concomitant treatment period:

The analysis of the primary endpoint will summarise DLT using descriptive statistics with the aim of determining the maximum tolerated dose (defined in Section 5.2.4 of the CTP) of:

- Afatinib in combination with TMZ when given concomitantly with RT (Regimen M);
- Afatinib when given concomitantly with RT (Regimen U).

An overall summary of AE occurrences with onset during the concomitant treatment period, which were defined to be DLTs by the investigator, will be presented. This will include the following AE attributes:

- Preferred term,
- Maximum CTCAE grade,
- Outcome,
- Time to first occurrence (relative to start of trial medication; see [Section 9.2](#) of this document).

Any AE meeting the criteria for DLT, regardless of date of onset, will be considered a significant adverse event (SIAE). The analysis of non-serious SIAEs and serious adverse events (SAEs) is described in [Section 7.8.1](#) of this document.

DLTs with onset after the concomitant treatment period will be listed separately.

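### A drug-related hepatic injury below CTCAE Grade 3 is managed under the DLT dose-reduction scheme, yet no stated rule counts it towards escalation or the MTD

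*Protocol*

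**What the plan says.** Protocol 5.2.5 lists DLTs as significant adverse events and adds a second kind: "Hepatic injury defined by the following alterations of liver parameters". With normal baseline liver tests the limits are AST and/or ALT at least 3x ULN with bilirubin at least 2x ULN in the same blood draw. With abnormal baseline the transaminase limit is 5x ULN. No CTCAE grade is attached. The event is reported in an expedited manner, and if the investigator judges "any protocol-specific significant event is related to study drug, the administration of the study drug must be managed according to section 4.1.4.1.2".

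Protocol 4.1.4.1.2 is written for DLTs. Its trigger is a "side effect that meets criteria for DLT (for definition refer to Section 5.2.3) regardless of treatment cycle, treatment with BIBW 2992 must be paused", and its table columns are the first, second and third DLT. A patient on 20 mg goes off-study at the first.

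The DLT list in protocol 5.2.3 has no liver item. The only entry that can capture a liver event is the catch-all, "All other non-hematological toxicities of CTCAEv3 Grade" 3 or above. Left ventricular function and renal function have their own items at Grade 2.

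Two rules govern replacement. In 4.1.4.1.1: "Patients who are not treated until the end of these 6 weeks for any reasons other than DLT will be replaced". In 6.3.1, patients who miss more than 5 consecutive or more than 8 non-consecutive days of treatment "for any reasons other than DLT will be replaced".

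The escalation table (4.1.4.1.1) and the MTD definition (5.2.4) use the DLT count alone. SAP 5.1 takes the primary endpoint from protocol 5.2.3. SAP 7.4 says: "Any AE meeting the criteria for DLT, regardless of date of onset, will be considered a significant adverse event (SIAE". The SAP does not name the hepatic category of 5.2.5.

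**The concern.** The protocol singles out one liver finding for expedited reporting and handles it, when related, through the scheme meant for DLTs. It does not say whether that finding is a DLT. If it is not, the handling may itself interrupt or end treatment for a reason other than DLT, and the replacement rules then take the patient out of the evaluable cohort. A drug-related liver signal at a dose would leave no trace in the tally that decides whether the next cohort opens and which dose is called the MTD. With cohorts of three and six, one omitted event matters.

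**Working it through.** **1. The plan's own figure.** Protocol 5.2.4 caps DLT incidence at the MTD at one in six: 1/6 = 16.7%, which rounds to the stated 17%. Two in six is 33%.

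**2. Where the gap lies.** The CTCAE limits for liver tests are not in the documents. Let Grade 3 start above T x ULN for AST/ALT and above B x ULN for bilirubin. Suppose the event is graded from these values. For normal baseline, an event that meets 5.2.5 but not 5.2.3 then has AST/ALT from 3 to T and bilirubin from 2 to B.

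- T = 5, B = 3 (assumed): AST/ALT 3-5x with bilirubin 2-3x ULN.
- T at or below 3, or B at or below 2: no gap, because every such event is then Grade 3 on at least one test.
- Abnormal baseline with T = 5: almost no gap, because 5.2.5 itself starts at 5x ULN.

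**3. What happens to a patient in the gap (event judged related).**

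| Situation | Rule | Place in the tally |
|---|---|---|
| Treatment ends before the 6 weeks are complete (at 20 mg the table says off-study) | 4.1.4.1.1 | Replaced |
| Pause of more than 5 consecutive or 8 total days, then resumption | 6.3.1 | Replaced |
| Shorter pause, or event first found at the Day 42 laboratory visit | Neither | Kept, DLT-free |

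Section 4.1.4.1.2 allows up to 14 days for recovery, so a permitted pause can fall on either side of the 5-day limit. In every row the event is missing from the DLT count.

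**4. Effect on one decision.** Counting one such event can turn 1/6 into 2/6, which stops escalation. It can also turn 0/3 into 1/3, which expands the cohort. Suppose two of the first five patients at 20 mg have such an event and both are replaced. The tally reads 0/3 and the rule says escalate. If both counted, there would be two DLTs at that dose and escalation would stop.

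**5. Effect on the probability of escalating.** Under 4.1.4.1.1 a dose is passed with 0/3, or with 1/3 followed by 0/3:

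P(escalate) = (1-x)^3 + 3x(1-x)^5

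Let p be the rate of listed DLTs and q the rate of related hepatic injury in the gap, taken as mutually exclusive. Then x = p+q if the events count, x = p/(1-q) if every such patient is replaced, and x = p if all are kept as DLT-free. The documents give no rates, so p and q are illustrative.

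For p = q = 0.10:
- replaced, x = 0.111: 0.702 + 0.185 = 0.887
- kept, x = 0.10: 0.729 + 0.177 = 0.906
- counted, x = 0.20: 0.512 + 0.197 = 0.709

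| p | q | Replaced | Counted |
|---|---|---|---|
| 0 | 0.10 | 1.000 | 0.906 |
| 0 | 0.20 | 1.000 | 0.709 |
| 0.10 | 0.02 | 0.903 | 0.871 |
| 0.10 | 0.05 | 0.897 | 0.814 |
| 0.10 | 0.10 | 0.887 | 0.709 |
| 0.10 | 0.20 | 0.862 | 0.494 |
| 1/6 | 0.10 | 0.741 | 0.564 |

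**6. Reporting.** SAP 6.3 uses the treated set for all analyses, and SAP 7 bases percentages on everyone in the set. In the example in step 4, the DLT table would show 0 of 5, with nothing to mark the two replaced patients.

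**The case against.** **The link to 4.1.4.1.2 does not make the event a DLT.** A reader might infer from it that hepatic injury is, or must be, a DLT. The documents do not support that. Section 4.2.3 also applies the dose-reduction scheme to persistent Grade 2 diarrhoea and Grade 2 nausea or vomiting, whose DLT items need Grade 3. Pausing and reducing for a non-DLT is normal in this protocol, and which toxicities limit dose is a clinical judgement. This stands, and it is why the point asks for reconciliation and not for a particular criterion.

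**The SAP does not exclude the event.** A reader might also infer that only DLTs can be SIAEs. The sentence in SAP 7.4 includes DLTs without excluding anything else, SAP 3 assumes familiarity with the protocol, and protocol 5.2.5 calls liver injury significant. SAP 7.8.1 plans a table of non-serious SIAEs and another of other significant AEs, and laboratory data follow a sponsor standard that is not in the documents. The event may therefore appear somewhere. What is missing is explicit wording that fixes where, and a display beside the DLT count.

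**The event would be seen.** Escalation needs the agreement of the sponsor's Trial Clinical Monitor, and hepatic injury is reported in an expedited manner. This is a real safeguard, but no stated criterion tells the monitor to count the event.

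**Rates and grade limits are assumed.** The protocol calls drug-induced liver injury rare, so the larger q values only show direction. At q = 0.02 with p = 0.10 the difference is about 0.03.

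**Conclusion.** The concern holds in a limited form. As written, a related hepatic injury that meets 5.2.5 but stays below Grade 3 is handled under the DLT scheme and omitted from the escalation and MTD tally, either by replacement or by counting the patient as DLT-free. The gap depends on the assumed grade limits: it disappears if Grade 3 starts at or below 3x ULN for transaminases or 2x ULN for bilirubin, and it is nearly empty for patients with abnormal baseline tests.

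Three stronger conclusions would go too far:
- **Replacement at 20 mg is not certain.** An event first found at Day 42 comes when the six weeks are complete, and 4.1.4.1.2 has a clinical-benefit exception, although its reach over the 20 mg off-study entry is unclear. At 30 or 40 mg replacement after a pause depends on its length.
- **One event does not by itself settle every dose level.** Moving from 0/3 to 1/3 only expands the cohort; moving from 1/6 to 2/6 does change the decision.
- **The effect is not always further escalation.** 40 mg is the ceiling, so there the consequence is a biased MTD count.

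Within those limits the omission works in one direction, towards a lower apparent DLT rate. It concerns a finding that the protocol itself treats as important.

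**What to change.** Reconcile protocol 5.2.3, 5.2.5, 4.1.4.1.2, 4.1.4.1.1 and 6.3.1. State whether a related hepatic injury as defined in 5.2.5 counts towards the DLT and MTD tally, and make the replacement rules consistent with the answer, so that a patient stopped for it is not silently replaced and dropped from the tally. The clinical choice is the sponsor's.

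In SAP 7.4 and 7.8.1, name the 5.2.5 hepatic injury explicitly as an SIAE and identify it from the AST, ALT and bilirubin values already collected. Show its count and any resulting replacements by regimen and dose cohort beside the DLT count, and give the MTD tally with and without these events. Two cross-references can be corrected at the same time: Appendix 10.8 cites a section 5.2.2.1 that does not exist, and SAP 7.8.1 cites protocol 5.2.2 for the DLT definition, which is in 5.2.3.

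The cost is a few lines of text, one extra table and possibly a slightly higher event count. No new data are needed.
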